#### **Primary outcome variable(s)**

A decrease in readmission rates of cirrhotic patients.

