# Continuing Review

## Basic Info

Confirmation Number: **chbgaide**  
Protocol Number: **828183**  
Created By: **[name]**  
Principal Investigator: **[name]**  
Protocol Title: **Use of A Telehealth Intervention to Decrease Readmissions in Cirrhosis: A Randomized Controlled Trial**  
Short Title: **Telehealth RCT in Cirrhotics**  
Protocol Description: **The proposed study is a randomized controlled trial comparing a simple telehealth intervention implemented after hospital discharge to standard of care for reducing hospital readmissions. All cirrhotic patients admitted to the Hepatology service at The Hospital of the University of Pennsylvania will be randomized to one of the two arms outlined above. Patients will be followed for 90 days. Rates of 30 and 90 day readmission will be compared between the groups.**  
Submission Type: **Social and Biological Sciences**  
Application Type: **FULL**

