## Protocol

### **Abstract**

To compare rates of 30 and 90-day readmission of cirrhotic patients to The Hospital of the University of Pennsylvania randomized to telehealth monitoring, as administered by the Way to Health Platform, or usual care. 2. To use a patient centered approach to determine the specific interventions which are most helpful as perceived by patients and have an impact on quality of life. Approximately 426 subjects will be enrolled.

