### **Objectives**

#### **Overall objectives**

1. To compare rates of 30 and 90 day readmission of cirrhotic patients to The Hospital of the University of Pennsylvania randomized to telehealth monitoring, as administered by the Way to Health Platform, or usual care. 2. To use a patient centered approach to determine the specific interventions which are most helpful as perceived by patients and have an impact on quality of life.

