#### **Secondary outcome variable(s)**

An improvement in patient, provider and caregiver satisfaction post-discharge.

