### Procedures

All cirrhotics admitted to the Hospital of the University of Pennsylvania between the ages of 18 and 80 will be approached for consent (see attached consent forms in the designated section of the protocol). If patients are missed due to being discharged on the weekend, during a holiday or timing issue, patients may be contacted by phone to enroll in the study. If interested, patients can give verbal consent over the phone or written consent at their following clinic visit. After consent is obtained and information is entered into the Way to Health Platform, the participant will be randomized. During this period of time, the participant will be asked to complete the quality of life assessments/ program surveys. Depending on the group to which they are randomized, those in the intervention group will receive welcome items (scale, stop watch, and binder, all necessary for proper data collection in the intervention group). Those randomized to the usual care arm will receive their standard discharge paperwork. Clinical data (readmissions, reasons for readmissions, and length of stay) will be determined for both groups at 30 and 90 days. The groups will additionally be asked to complete quality of life assessments at the end of the study period and a program assessment in the middle and end of the protocol. Additionally, as assessment of readmission rates will be determined in both groups for another 90 days after the end of the intervention (to determine if the health behaviors learned in the intervention group are durable and to determine if providing the intervention to those in the usual care arm is beneficial even if there is a delay in initiation).

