**Analysis Plan**

The primary analysis will include a comparison of the demographics and clinical data for the intervention group and the usual care group. To determine if there is a difference in the rates of readmission between the groups, univariable logistic regression analysis will be performed. Any predictors which were different between the groups will be used for adjustment in a multivariable logistic regression. We plan to analyze the data at the 6 month mark. If a significant difference is found, given the low cost of the intervention and potential benefits, the study will be stopped and all patients admitted to the hepatology service will be eligible for telehealth monitoring. Data for the secondary outcomes including changes in quality of life and patient satisfaction will be explored.

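### 30-day and 90-day readmission are both compared but not ranked, and neither the primary outcome nor the 6-month stopping rule says which one decides

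*Protocol*

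**What the plan says.** The two windows appear together in four places, never in rank order:

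- Protocol, Basic Info (Protocol Description): "Rates of 30 and 90 day readmission will be compared between the groups".
- Protocol, Abstract: "To compare rates of 30 and 90-day readmission of cirrhotic patients".
- Protocol, Overall objectives, objective 1: "To compare rates of 30 and 90 day readmission of cirrhotic patients".
- Protocol, Procedures: readmissions, their reasons and length of stay "will be determined for both groups at 30 and 90 days".

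The fields that should settle the order do not:

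- Primary outcome variable(s): "A decrease in readmission rates of cirrhotic patients". No window is given.
- Secondary outcome variable(s): "An improvement in patient, provider and caregiver satisfaction post-discharge". Neither readmission window is listed.
- Analysis Plan, main comparison: "To determine if there is a difference in the rates of readmission between the groups, univariable logistic regression analysis will be performed". No window is given.
- Analysis Plan, interim: "We plan to analyze the data at the 6 month mark". The next sentence stops the study if the groups differ significantly, again without a window.

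Procedures also adds a third readmission assessment, covering a further 90 days after the intervention ends. Its stated purposes are to see whether learned behaviours last and whether delayed telehealth helps the usual care arm.

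**The concern.** The protocol sets a primary outcome and a binding stopping action, but no single defined test stands behind either. If the 30-day result were significant at 6 months and the 90-day result were not, or the reverse, the document would not say whether to stop. The same gap applies to the final conclusion.

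The setting makes this matter more. The Design section states that there is no blinding, and Data and Safety Monitoring gives the monitoring to the principal investigator and co-investigator, without a DSMB. Data Management passes a de-identified dataset to a biostatistician, but de-identification does not fix the window. A window named after results are known cannot be shown to be independent of them.

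The statistical stake is the false-positive rate. Two chances at an unadjusted 0.05 give more than 5% error overall.

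**Working it through.** **Which window did the sample size use?** The target of 426 (Abstract) comes with no effect, alpha, power or window, so it cannot be reproduced. Combinations on either window come close. With two-sided 0.05, 28% against 15% at 90% power and no dropout gives 416, and 53% against 37% at 90% power and 5% dropout gives 426. The figure therefore does not reveal the intended window, and it is not shown to be wrong.

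**Inputs for the error calculation**
- 30-day rate 28%: Background, this hospital's own figure.
- 90-day rate 53%: Background, pooled over a 14-centre consortium that includes this centre.
- 213 per arm: 426 / 2, from the 1:1 allocation.
- Two-sided 0.05 per window, with either window sufficient for success: assumptions, not stated in the protocol.

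**Step 1: correlation of the two tests under the null.** A patient readmitted by day 30 is also readmitted by day 90, so the indicators are nested:

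rho = sqrt[ p30(1 - p90) / ((1 - p30) p90) ] = sqrt[ (0.28 x 0.47) / (0.72 x 0.53) ] = sqrt(0.1316 / 0.3816) = 0.587.

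**Step 2: chance that at least one test is significant.** With (Z1, Z2) bivariate normal and correlation 0.587:

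1 - P(|Z1| < 1.96 and |Z2| < 1.96) = 0.088.

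Simulating 213 per arm with a pooled z-test gives 0.085. It is slightly lower because the single 90-day test runs at about 0.047. For comparison, independent tests would give 1 - 0.95 x 0.95 = 0.0975.

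**Step 3: sensitivity to the 90-day rate, with 30 days held at 28%.** The range is arbitrary.

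| 90-day rate | Either window significant at 0.05 |
|---|---|
| 35% | 7.5% |
| 53% | 8.8% |
| 62% | 9.1% |

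**Step 4: alpha split.** With 0.025 per window and rho = 0.587, the overall error is 0.045.

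**Step 5: what each choice means at the 6-month look.** Study duration gives about one year in total with 90 days per participant, so accrual is at most about 12 - 3 = 9 months. With even accrual over 9 months:

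- 90-day outcome complete: (6 - 3) / 9 = 33%, or 142 of 426.
- 30-day outcome complete: (6 - 1) / 9 = 56%, or about 237 of 426.

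The error figures in Steps 2 to 4 are for the final analysis only and exclude the 6-month look.

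**The case against.** **The SAP may settle it.** The SAP is not shown, and the order of endpoints, the success rule and the outcome for each regression are often written there. This has weight for the regression details. It does not cover the primary outcome field or the stopping sentence, because the protocol fixes both itself and leaves the window out.

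**The reader is not left without any window.** Read with objective 1, the primary outcome most naturally means both 30 and 90 days. This stands: it would be too strong to infer that no time frame was intended. What is missing is the order of the two and what counts as success.

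**The inputs are soft.** The 53% is a pooled figure, and no source in the protocol supports 35% or 62% as bounds for the 90-day rate (the 62% in Background carries no window). This also stands. The error figures are therefore illustrations, though every value tried exceeds 5%.

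**Stronger readings.** A reader might infer that the trial loses power because both windows must succeed. No such rule, and no target effect, appears in the protocol, so no power loss can be asserted. A reader might also infer that 426 is wrong or was based on the wrong window. The document gives too little to show either.

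**Conclusion.** The point holds in a limited form. Both windows are meant, neither is ranked, and the stopping rule acts on an undefined one. If either window may succeed at an unadjusted two-sided 0.05, the false-positive rate at the final analysis is about 8.5-8.8% instead of 5%, assuming 213 per arm and null rates of 28% and 53%. Over an arbitrary range of 35-62% for the 90-day rate it is 7.5-9.1%.

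The documents do not show that anyone intends to pick the window after seeing results, only that nothing in the protocol prevents it. The absence of an alpha adjustment for the 6-month look is a separate matter and is not part of this figure.

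**What to change.** **Primary outcome variable(s).** Name one window, for example: the primary outcome is the proportion of patients readmitted within [30 or 90] days of discharge. List the other under Secondary outcome variable(s). Alternatively, if either window may succeed, declare two primary endpoints tested at 0.025 each (overall error about 4.5% under the assumptions above).

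**Analysis Plan.** Tie the primary regression and the 6-month stopping rule to the named outcome, before any data are looked at.

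**Procedures.** State that the further 90-day post-intervention readmission assessment is secondary.

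**Choosing the window.** Ninety days matches the follow-up period, and 30 days is the window of the hospital's own quoted rate. Key inclusion criteria, Subject recruitment, Procedures and the Consent overview allow consent, and so randomisation, after discharge. Part of a 30-day window counted from discharge may therefore precede randomisation.

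**Cost.** The change is a few words and needs no new patients, visits or data. The window not chosen can no longer be claimed as confirmatory on its own. A 90-day primary has about one third of patients complete at the 6-month look, against about 56% for 30 days, with accrual over about 9 months. The change neither controls the error from the unadjusted 6-month look nor makes 426 checkable.

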#### **Secondary outcome variable(s)**

An improvement in patient, provider and caregiver satisfaction post-discharge.

### **Background**

It is well known that patients with cirrhosis have high morbidity and mortality and that early re-hospitalization in any disease process is known to be costly and partially preventable. Few studies exist in the literature on the topic of readmissions in cirrhosis and none use a patient centered approach or a telehealth strategy to reduce readmissions and improve quality of care nor impact quality of life. Volk et al. demonstrated in 2012 that rates of hospital readmission among patients with cirrhosis are higher than other diseases such as CHF, making this patient group at high risk for poor health outcomes. Predictors of readmission include Model For End Stage Liver Disease, MELD, score, serum sodium, and number of concomitant medications used. Frequent readmissions are independently associated with increased mortality, making this not just an economic but also a human concern. The 1st and 2nd most common causes for readmission in cirrhotics are fluid imbalances (overload or dehydration) and hepatic encephalopathy (HE) or confusion resulting from liver disease. Overt HE occurs in 30-40% and minimal HE in 20-80% of patients with cirrhosis. It presents a unique clinical challenge not present in most populations with severe underlying medical conditions as confusion can lead to poor adherence with treatment, making cirrhotics arguably one of the highest risk populations for poor health outcomes. Unfortunately, little attention has been paid to this area thus far. More recently the NACSELD consortium, a 14 center group of liver transplant centers including Penn, showed a 53% 90-day readmission rate for cirrhotics (Bajaj et al). Discrete data from the consortium is limited compared to that from single center studies and no intervention was performed to decrease readmissions or improve patient involvement in their care through this consortium. Authors Tapper, Kumral and Fortune have shown in the last year that readmission rates of cirrhotics at their liver transplant centers are 38%, 62%, and 40%. At The Hospital of the University of Pennsylvania, the 30-day readmission rate for cirrhotic patients is 28%. The hepatology service at the Hospital of The University of Pennsylvania has the highest percentage of potentially preventable readmissions (PPRs) of any service (23.3%) and

approximately 50% of PPRs return within 10 days of discharge. There is significant room for improvement. The cost of hospital readmissions in the United States is a focus of Medicare and private insurance companies alike with an estimated cost of unplanned readmissions in Medicare recipients of \$17.4 billion in year 2004 alone. As this comprised 20% of the Medicare hospital payments made, readmission rates are now considered a national quality indicator. Patients with cirrhosis and ascites comprise a large percentage of hospital admissions. At the University of Pennsylvania, as a large transplant center, an average of 54-65 cirrhotic patients are admitted to the hepatology service every month. Many admissions are due to poor medication adherence and a lack of early detection of clinical deterioration. This study will help to determine rates of 30 and 90-day readmissions and examine the impact of a simple telehealth intervention compared to usual care. In a pilot study, we were the first group to explore telehealth interventions in cirrhosis and the first to examine patient involvement and social support tools to decrease readmissions in cirrhosis. It is our hope that testing this intervention in a randomized controlled trial, further refining the intervention and addressing gaps in knowledge will help to bridge gaps in care. We believe that this patient centric approach will provide the most useful information on which to base future clinical care models and to optimize patient centered interventions.

### ***Study Design***

#### **Phase\***

Not applicable

#### **Design**

A randomized controlled trial will be conducted. The 2 potential groups to which patients may be randomized are: 1) a simple telehealth intervention that utilizes the Way to Health Platform to send SMS messages directly, and 2) standard of care. Given that assignment to the interventions will be obvious to the participants, study staff and investigators, no blinding procedures will be employed. Of note, any participant randomized to the usual care arm will be offered 90 days of telehealth monitoring after study completion.

#### **Study duration**

The estimated length of the study will be approximately one year. Each participant will be enrolled for a period of 90 days. The period of follow up will begin on the discharge day and end exactly 90 days from that date. Once patients have completed the 90 days of observation, they are not permitted to be re-enrolled in the study. If a control patient chooses to receive telehealth text messages after the 90 days, they will be in the study for up to 180 days.

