**The following documents are currently attached to this item:**

*There are no documents attached for this item.*

**If there is subject compensation, provide the schedule for compensation per study visit or session and total amount for entire participation, either as text or separate document**

All participants, regardless of which arm to which they are randomized, will receive \$25 after 30 days of enrollment and \$25 after 90 days of enrollment (end of observation period) as long as they remain enrolled in the study. Therefore, all participants will receive a total of \$50 for compensation. Compensation will be provided to participants via the Way to Health Platform via a check generated and sent to their home, assuming participants are willing to provide their social security number and any other additional information required.

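### Follow-up starts at discharge for everyone, but patients consented afterwards are randomised later, so their window includes days before assignment and the two stated 90-day periods disagree

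*Protocol*

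**What the plan says.** Protocol, Study duration, gives two statements about the same period. One is "Each participant will be enrolled for a period of 90 days". The next fixes the dates: "The period of follow up will begin on the discharge day and end exactly 90 days from that date".

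Protocol, Subject compensation, counts from enrolment instead. Payments fall due "after 30 days of enrollment" and "after 90 days of enrollment (end of observation period"), so the second payment date is equated with the end of observation.

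Protocol, Procedures, says that readmission data "will be determined for both groups at 30 and 90 days", with no origin given. The same section states that for those missed before leaving hospital, "patients may be contacted by phone to enroll in the study", and that "patients can give verbal consent over the phone or written consent at their following clinic visit". It then sets the order of events: "After consent is obtained and information is entered into the Way to Health Platform, the participant will be randomized".

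Two other sections confirm the late route. Subject recruitment includes scheduled clinic visits as a setting. The Consent Process overview describes pre-discharge interviews as the primary route, but plans a telephone attempt in the first week after discharge for those who did not consent in hospital. The inclusion criteria accept an admission, here or at another hospital, during the preceding 30 days.

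**The concern.** The two 90-day periods agree only for a patient enrolled on the day of discharge. For anyone consented later, discharge precedes randomisation by days and possibly weeks, and no section moves the origin for that group.

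Two things follow:

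- **Days before assignment.** Part of the outcome window lies before the patient has been assigned. Telehealth cannot prevent a readmission that has already happened. If such readmissions count, they add equal risk to both arms and pull the contrast toward no effect. If those days are event-free by construction, because a readmitted patient is not enrolled or gets a new index discharge, the relative effect is essentially kept but there are fewer events.
- **Two end dates.** The end of observation differs between the study-duration and compensation sections. It also governs when usual-care patients may be offered telehealth (Group Modifications). If the offer is made 90 days after discharge while observation runs to 90 days of enrolment, a control patient could receive the intervention inside the longer window.

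**Working it through.** **Which windows disagree.** For a patient randomised *L* days after discharge, the discharge-based window ends on day 90 and the enrolment-based window on day 90 + *L*. The share of each outcome window that precedes assignment is *L*/30 and *L*/90.

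| Lag *L* | Share of 30 days | Share of 90 days | End of 90 days of enrolment |
|---|---|---|---|
| 7 days | 23% | 8% | day 97 |
| 14 days | 47% | 16% | day 104 |

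The inclusion criterion on recent admission keeps *L* below about 30 days.

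**Inputs for the effect on power.**
- From the protocol: 426 patients allocated 1:1, so 213 per arm; 28% site readmission at 30 days; 53% at 90 days from a consortium; about half of potentially preventable readmissions back within 10 days.
- Assumed: hazard ratio 0.6, two-sided 0.05, the share of late enrollees and their delay. The protocol gives no target effect, alpha or power behind 426, so there is no stated power to reproduce.

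**Formulas.** Cumulative hazard H(30) = −ln(0.72) = 0.3285; H(90) = −ln(0.47) = 0.7550. For a late enrollee randomised on day *d*, over a window of length T:
- *Counted* (readmissions before randomisation are outcomes): control 1 − exp(−H(T)); intervention 1 − exp(−[H(d) + 0.6(H(T) − H(d))]).
- *Event-free* (no readmission possible before randomisation): control 1 − exp(−[H(T) − H(d)]); intervention 1 − exp(−0.6[H(T) − H(d)]).

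Arm risks are share-weighted averages over on-time and late patients. Power is the pooled two-proportion normal approximation.

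Two hazard shapes are used. Under a constant hazard, H(7) = 0.3285 × 7/30 = 0.0767. The front-loaded shape puts half of the 30-day hazard in the first 10 days, so H(7) = 0.3285 × 0.5 × 7/10 = 0.1150. It applies to all readmissions a pattern that the protocol gives only for preventable ones.

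**Worked case: 20% randomised on day 7, counted, constant hazard.** On-time intervention risk is 1 − exp(−0.6 × 0.3285) = 17.9%. Late intervention risk is 1 − exp(−[0.0767 + 0.6 × 0.2518]) = 20.4%. The average is 0.8 × 17.9 + 0.2 × 20.4 = 18.4%, against 28.0% in control. The risk ratio moves from 0.639 to 0.657.

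**30-day power (constant / front-loaded).**

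| Scenario | Counted | Event-free |
|---|---|---|
| No delay | 0.700 | 0.700 |
| 10% on day 7 | 0.677 / 0.665 | 0.691 / 0.685 |
| 20% on day 7 | 0.653 / 0.629 | 0.681 / 0.669 |
| 30% on day 14 (outer case) | 0.555 / 0.514 | 0.633 / 0.608 |

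With 20% on day 7, the event-free risk ratio stays at 0.637 under both hazard shapes, so the loss there comes from fewer events. Nothing in the protocol suggests that the outer case is likely.

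**90-day power.** With no delay the risks are 53.0% and 36.4%, power 0.933. With 20% on day 7 it is 0.925 / 0.916 counted and 0.931 / 0.928 event-free.

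**After re-anchoring (20% on day 7, 30-day window from randomisation for late enrollees).** Under constant hazard the power returns to 0.700. Front-loaded, the late hazard over days 7 to 37 is 0.3285 + (0.7550 − 0.3285) × 7/60 − 0.1150 = 0.2633, giving 27.0% against 17.2% and power 0.684. The gain is 4.7 / 5.5 points over counted and 1.9 / 1.5 points over event-free. The front-loaded re-anchored and 90-day figures join the 28% and 53% rates, which come from different sources; that is an assumption.

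**The case against.** Discharge is the natural origin for a readmission rate. It is the origin behind the usual 30-day metric and the site's 28%, and it is applied identically in both arms, so it creates no bias in favour of either. The rival window comes mainly from a payment schedule, and the statement about 90 days of enrolment can be read as explained by the sentence that follows it. How to count a readmission between discharge and randomisation is an endpoint-derivation rule that an SAP could hold. Most patients are recruited before discharge, and the late share, the delay and the hazard ratio are all assumed.

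Much of this stands. There is no bias toward either arm, the power figures are illustrations, and the absence of a counting rule should carry no weight by itself while the SAP is not shown. Two things remain. The protocol itself fixes a discharge origin while allowing randomisation after discharge, so for late enrollees the stated window includes days before assignment. And the compensation section names a different end of observation from the study-duration section. Both are statements in the protocol, not gaps left for another document.

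**Conclusion.** The concern holds, as a minor point. For patients consented after discharge, the fixed follow-up window includes time before assignment and disagrees with the 90 days of enrolment.

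Type I error is intact and the direction of any effect is toward no difference or fewer events. With 10% to 20% of patients randomised on day 7, the illustrative loss of 30-day power is about 1 to 7 points (0.70 down to between 0.69 and 0.63), depending on how early readmissions are treated and on the shape of the hazard. At 90 days, with 20% on day 7, it is under 2 points. These sizes rest on an assumed hazard ratio of 0.6 and on late shares and delays that the protocol does not give. The mismatch between the two windows does not depend on any of those assumptions.

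**What to change.** Use one time origin throughout the protocol:

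- Define the index discharge as the last discharge before randomisation, or the discharge from the current stay for a patient randomised as an inpatient.
- Set time zero as the later of index discharge and randomisation. This also settles the opposite case, in which an inpatient is enrolled some days before leaving hospital.
- Count only readmissions after time zero, over 30 and 90 days, in both arms.
- Reword Study duration and Subject compensation to this window, and give the origin for the 30- and 90-day assessments in Procedures.
- Keep the discharge-anchored 30-day rate as a supporting analysis.

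The cost is wording and a patient-specific chart-review window, with no extra patients or visits. The drawback is that, for late enrollees, the main 30-day rate departs from the discharge-based metric behind the 28% benchmark; the supporting analysis covers that. If the sponsor prefers to keep discharge as the origin, the study-duration and compensation sections must still be reconciled to one end date.
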